4.5.2. Plan for Review of Pauses and Resuming Rules

The IND Sponsor with participation by the PSRT, will conduct the review and make the decision to resume, amend or close the study. As part of the pause review, the reviewers will also advise on whether the study needs to be paused again for any subsequent AEs of the same type.

Enrollments and study product administration would resume only if review of the AEs that caused the pause result in a recommendation to permit further study injections and enrollments. When indicated, safety data reports and changes in study status will be submitted to relevant regulatory authorities including the IRB in accordance with [Section 5.3](#) and institutional policy.

5. SAFETY AND ADVERSE EVENTS

5.1. Adverse Events

An adverse event (AE) is any untoward or unfavorable medical occurrence in a human subject, including any abnormal sign (e.g., abnormal physical exam or laboratory finding), symptom, or disease temporally associated with the use of study treatment, whether or not considered related to the study treatment.

AEs will be graded according to the Table for Grading Severity of AEs ([Appendix IV](#)). The following guidelines will be used to determine if an AE should be recorded in the database:

- Solicited AEs (i.e. reactogenicity parameters) will be recorded in the study database for 7 days after each study injection without the collection of product attribution assessments.

Clinicians will follow and collect resolution information for any reactogenicity symptoms that are not resolved within 7 days.

- Unsolicited AEs will be recorded in the study database from the date of receipt of each study injection through the visit scheduled at 28 days after each injection with the collection of product attribution assessments. At other time periods between injections and when greater than 28 days after the last injection, only SAEs (as detailed in [Section 5.2](#)) and new chronic medical conditions will be recorded as an AE through the last study visit.

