Vaccines to prevent RSV mediated disease are both urgently needed and uniquely challenging. In the late 1960s, a formalin-inactivated RSV vaccine (FI-RSV) was associated with enhanced disease following subsequent RSV infection [22]. Among FI-RSV vaccine-immunized infant subjects (n=31), 80% required hospitalization following infection and two deaths were reported. This is compared to 5% requiring hospitalization following infection and no deaths among the parainfluenza vaccine-immunized control infants (n=40). Severe RSV disease was found to be more frequent in vaccinees than in the same-age general population not enrolled in the vaccine study [23-25]. Because infants and small children are a primary target population for an effective RSV vaccine, the legacy from that trial represents a substantive obstacle for development of an RSV vaccine for antigen-naïve infants.

Unique properties of RSV have provided challenges to the development of a successful vaccine. RSV encodes three envelope proteins, a small hydrophobic (SH) protein of unknown function, an attachment glycoprotein (G), and a fusion (F) protein. Of these proteins, only the F protein is essential for infecting cells *in vitro*; although, *in vivo*, G protein expression provides an advantage for infection of human airway epithelia [26]. The G protein is more variable than any other RSV protein and a high proportion of G is secreted through an alternative translation

initiation site, and acts as an immunomodulatory decoy for adaptive immune responses [27]. Non-structural RSV gene products, NS1 and NS2, both interfere with innate immune responses through cooperative inhibition of interferon induction and effector functions [28, 29].

RSV lacks an optimal animal model. Rodent models such as mice and cotton rats are only semi-permissive for RSV infection, although they are useful for defining immune response patterns and rank-ordering candidate vaccines for neutralizing potency and protective capacity. Nonhuman primates (NHP) are useful for immunogenicity and challenge studies, but possess variable levels of susceptibility to infection and generally require large inocula intranasally and intratracheally to consistently establish infection.

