4.2.5. Follow-Up through End of Study

Study follow-up will continue via clinical visits through 44 weeks after the first study injection. The visit schedule is based on intervals of time after each study injection administration. Any subject who receives at least one study injection (including those subjects who elect not to

receive the optional second dose) will be expected to continue with follow-up for safety and immunogenicity through study Week 44 as per Schedule of Evaluations (Appendix III).

Throughout the study, any subject who is suspected of having an upper respiratory infection based on the presence of rhinorrhea in conjunction with at least one additional sign and/or symptom should be evaluated by nasal flock swab for PCR diagnostic purposes.

The schedule of visits, allowable windows for completing the visits, and evaluations performed at each visit are shown in the Schedule of Evaluations in Appendix III. After Day 0, deviations from the visit windows in completing study visits are discouraged and will be recorded as protocol deviations, but are permitted at the discretion of the PI.

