6.2. Endpoints

6.2.1. Primary Endpoints: Safety

Assessment of product safety will include clinical observation and monitoring of hematological and chemical parameters. Reactogenicity will be closely monitored for 7 days after each product administration and safety evaluated by clinical visits through the study duration.

The following parameters will be assessed:

- Local reactogenicity signs and symptoms
- Systemic reactogenicity signs and symptoms
- Laboratory measures of safety
- Adverse events
- Serious adverse events
- New chronic medical conditions

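### Respiratory illness is PCR-swabbed for 44 weeks, but non-serious RSV illness outside the 28-day windows has no stated route into the safety tables

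*Combined protocol and SAP*

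**What the plan says.** Three parts of the protocol bear on this.

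- **Detection, Section 4.2.5.** "Study follow-up will continue via clinical visits through 44 weeks after the first study injection". The same section adds: "Throughout the study, any subject who is suspected of having an upper respiratory infection based on the presence of rhinorrhea", together with at least one other sign or symptom, "should be evaluated by nasal flock swab for PCR diagnostic purposes". It does not name the PCR targets, say where results are stored, or define a case.
- **Recording, Section 5.1.** Unsolicited adverse events go into the study database from each injection "through the visit scheduled at 28 days after each injection with the collection of product attribution assessments". After that: "At other time periods between injections and when greater than 28 days after the last injection, only SAEs" (as Section 5.2 defines them) "and new chronic medical conditions will be recorded as an AE through the last study visit". No exception is made for respiratory or RSV illness.
- **Endpoints and analysis, Sections 6.2 and 6.4.** Section 6.2.1 introduces the primary safety endpoint with "safety evaluated by clinical visits through the study duration". It then lists reactogenicity, laboratory measures, adverse events, serious adverse events and new chronic conditions. Section 6.4.2 tabulates recorded adverse events. The PCR results appear in no primary, secondary or exploratory endpoint and in no analysis.

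**The concern.** The plan asks for respiratory illness to be tested over the whole study, but its recording rule admits the non-serious findings for only a small part of that time. RSV illness follows exposure and season, so there is no reason for it to fall within 28 days of an injection.

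For an RSV vaccine given to humans for the first time, the number, timing and grade of confirmed RSV illnesses among vaccinees is an obvious item for the safety report. As written, a confirmed illness at Week 20 that is neither serious nor a new chronic condition would be swabbed but would not enter the adverse event tables. That could include some Grade 3 illness: the general Grade 3 definition in Appendix IV does not require hospitalisation, which first appears at Grade 4.

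At stake is the completeness of the safety record. No sample size or stated probability is affected.

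**Working it through.** **Inputs from the documents**
- Follow-up is 44 weeks (Sections 4 and 4.2.5), with the last visit at Day 308 (Appendix III).
- Full recording of unsolicited events lasts 28 days after each injection (Section 5.1).
- Injections are at Day 0 and Day 84 (Section 4, Appendix III). The second is optional for the last 5 subjects in each of 6 groups, so up to 5 × 6 = 30 of the planned 90 may have one injection.
- Visit windows are ±3 days for the 28-day visits, ±7 days for the Week 12 visit and ±7 days for the last visit, which is timed from the Week 12 visit (Appendix III).

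**The plan's own figures.** 44 × 7 = 308 days, which matches Day 308. The zero-event bounds in Section 6.3.1 also reproduce as 1 − 0.025^(1/n): 30.9% for n = 10 (stated as 31%), 21.8% for n = 15, and 11.6% for n = 30 (stated as 12%). These bounds presuppose that an event, if it occurs, is recorded.

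**Time under the restricted rule**
- Two injections: Day 28 to 84 (56 days) plus Day 112 to 308 (196 days) = 252 days. 252/308 = 81.8%; full recording covers 56/308 = 18.2%.
- One injection: Day 28 to 308 = 280 days. 280/308 = 90.9%; full recording covers 28/308 = 9.1%.
- 60 subjects with two injections and 30 with one: 1 − (60 × 56 + 30 × 28)/(90 × 308) = 1 − 4,200/27,720 = 84.8% of person-time.
- Range over the visit windows, two injections: 1 − 62/294 = 78.9% to 1 − 50/322 = 84.5%. One injection: 1 − 31/294 = 89.5% to 1 − 25/322 = 92.2%.

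**Does season change this?** The documents give no RSV season and no enrolment calendar, so this is an assumption shown as a range. Take one season of 90, 120, 150 or 180 days a year and all 365 possible start dates, with two injections.
- Pooled over evenly spread start dates, the share of in-season days under the restricted rule stays at 81.8%.
- With a season of 120 to 180 days, it is at least 50% for every start date.
- With a 90-day season, it is above 50% for 89% of start dates and falls to 15% at worst. The worst case is a start with 28 season days left: the next season opens on Day 28 + 275 = 303, so only 5 of the 33 in-season days fall outside the windows (5/33 = 15%).

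**Possible counts.** The documents give no adult RSV rate. If 3% to 10% of subjects had symptomatic RSV over 44 weeks, evenly spread, then 90 × 0.03 = 2.7 to 90 × 0.10 = 9 would be ill. Of these, 2.7 × 252/308 = 2.2 to 9 × 252/308 = 7.4 would fall under the restricted rule. Any that were serious would still be recorded, so these figures are upper values for the illnesses missed. Per group the total is 2.7/6 = 0.45 to 9/6 = 1.5 illnesses.

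**The case against.** Several points on the other side stand.

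- **The information need not be lost.** Section 5.1 governs what is entered in the database as an adverse event. Section 9.3.3 keeps laboratory reports and medical records as source data, Appendix III schedules medical history at visits to Week 44, and under Section 8.8.1 the safety review team looks at safety reports at least monthly to the end. A reader might infer that swab results are discarded; the text does not say so. What remains is that the statistician works from data extracted from the data management system (Section 9.3.1), and no field or analysis for these results is described.
- **Serious illness is captured.** Serious adverse events are recorded through the last visit. The definition in Section 5.2.1 reaches beyond hospitalisation, so some Grade 3 illness could qualify. The gap is confined to illness that does not.
- **Section 6.2.1 is not contradicted.** Its list includes serious events and new chronic conditions, which are collected to Week 44.
- **Enhanced disease.** A reader might infer that the protocol names this as a hazard of DS-Cav1. It does not. The Introduction reports that "a formalin-inactivated RSV vaccine (FI-RSV) was associated with enhanced disease following subsequent RSV infection", but that is a different product given to infants, and the obstacle it describes concerns antigen-naïve infants. This trial enrols adults aged 18 to 50, and the Introduction says nearly everyone has had RSV by age three. Section 8.5.1 bases the risks of DS-Cav1 on vaccines in general.
- **Detecting a shift in severity.** A reader might expect fuller recording to reveal milder illness becoming more severe. With about 0.45 to 1.5 illnesses per group on the assumption above, and every subject vaccinated, it could not.
- **The swab trigger.** Section 4.2.5 states when a swab is called for and does not bar testing of other presentations. This point needs no wider trigger.

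None of this supplies a route from a confirmed non-serious illness to the safety tables.

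**Conclusion.** The gap is real and modest. For about 82% of follow-up after two injections and 91% after one, a PCR-confirmed RSV illness that is neither serious nor a new chronic condition has no stated route into the safety tables, and no planned analysis uses the PCR results. These shares follow from the protocol's own schedule.

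That most such illnesses would fall in this time is an inference from person-time. It holds under an even hazard and for most seasonal patterns tried, but not for every start date with a short season. The illness counts rest on an assumed 3% to 10% rate. The point also assumes that the PCR covers RSV, which Section 4.2.5 leaves unstated.

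This is an inexpensive improvement to the safety record. It does not undermine the primary objective.

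**What to change.** Add one exception to Section 5.1: every PCR-confirmed RSV illness found under Section 4.2.5 from Day 0 through Week 44 is entered in the study database, whatever its severity or timing, with onset, duration, Appendix IV grade and days since the last injection. The 28-day rule stays as it is for all other non-serious events. Confirm at the same time that RSV is among the PCR targets.

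Add one descriptive listing or table to Section 6.4.2 showing these illnesses by group and by number of injections received. State there that it is descriptive and is not a test for enhanced disease.

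The cost is one sentence, one database form, one table and a few extra records; the swabs are already called for. Section 1.3 reports 95 subjects enrolled by August 2019, so for time already elapsed the entries would have to be made retrospectively from source records. Completeness may be uneven there, and the table should say so. Sample size and the precision figures in Section 6.3.1 do not change.

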5.2. Serious Adverse Events

5.2.1. Serious Adverse Event Definition

The term “serious adverse event” (SAE) as defined in 21 Code of Federal Regulations (CFR) 312.32 as follows: “an adverse event or suspected adverse reaction is considered "serious" if, in the view of either the investigator or sponsor, it results in any of the following outcomes: Death, a life-threatening adverse event, inpatient hospitalization or prolongation of existing hospitalization, a persistent or significant incapacity or substantial disruption of the ability to conduct normal life functions, or a congenital anomaly/birth defect. Important medical events that may not result in death, be life-threatening, or require hospitalization may be considered serious when, based upon appropriate medical judgment, they may jeopardize the patient or subject and may require medical or surgical intervention to prevent one of the outcomes listed in this definition. Examples of such medical events include allergic bronchospasm requiring intensive treatment in an emergency room or at home, blood dyscrasias or convulsions that do not result in inpatient hospitalization, or the development of drug dependency or drug abuse.”

“Life threatening” refers to an AE that at occurrence represented an immediate risk of death to the subject. An event that hypothetically may cause death if it occurs in a more severe form is not considered life-threatening. Similarly, a hospital admission for an elective procedure is not considered a SAE.

5.2.2. Reporting Serious Adverse Events to the IND Sponsor

AEs that meet SAE Reporting Requirements must be reported by the clinical site and submitted on an expedited basis to the IND Sponsor, according to sponsor guidelines as follows:

- results in death;
- is life-threatening;
- results in persistent or significant disability/incapacity;
- requires unplanned inpatient hospitalization or prolongation of existing hospitalization;
- is a congenital anomaly/birth defect in the offspring of a study subject; or,
- is an important medical event that may jeopardize the subject or may require intervention to prevent one of the other outcomes listed above.

Additionally, any event, regardless of severity, which in the judgment of a PI represents a SAE, may be reported on an expedited basis.

An investigator will communicate an initial SAE report within 24 hours of site awareness of occurrence to the IND Sponsor by email to the VRC Protocol Operations Office (Appendix II). A written report by the investigator should be submitted to the IND Sponsor within 3 working days. In order for the IND Sponsor to comply with regulations mandating sponsor notification of specified SAEs to the FDA within 7 or 15 calendar days, the investigator must submit additional information as soon as it is available.

5.2.3. IND Sponsor Reporting to the FDA

It is the responsibility of the IND Sponsor to make the determination of which SAEs are “serious and unexpected suspected adverse reactions” (SUSARs) as defined in 21 CFR 312.32.

- *Suspected adverse reaction* means any AE for which there is a reasonable possibility that the drug caused the AE.
- *Unexpected adverse event* means an AE that is not listed in the IB or is not listed at the specificity or severity that has been observed.

All SUSARs, as determined by the IND Sponsor, will be reported to the FDA as IND Safety Reports. All IND Safety Reports will be provided to the IRB.

The IND Sponsor will also submit an IND Annual Report of the progress of the investigation to the FDA as defined in 21 CFR 312.33.

5.3. Reporting to the Institutional Review Board

The following information is consistent with NIH IRB Policy 801: Reporting Research Events, Version 1, effective July 1, 2019.

Reportable Event - An event that occurs during the course of human subject research that requires notification to the IRB.

For the purposes of this policy, reportable events include the following:

- Unanticipated Problems (UPs) involving risks to subjects or others,
- Non-compliance (including major protocol deviations and noncompliance that is not related to a protocol deviation),
- Deaths related or possibly related to research activities, and
- New information that might affect the willingness of subjects to enroll or continue participation in the study.

5.3.1. Unanticipated Problem

An unanticipated problem (UP) is defined as any incident, experience, or outcome that meets **all** of the following criteria:

- Unexpected (in terms of nature, severity, or frequency) given (a) the research procedures that are described in the protocol-related documents, such as the IRB

approved research protocol and informed consent document; and (b) the characteristics of the subject population being studied; **and**

- Related or possibly related to participation in the research (possibly related means there is a reasonable possibility that the incident, experience, or outcome may have been caused by the procedures involved in the research); **and**
- Suggests that the research places subjects or others (which may include research staff, family members or other individuals not directly participating in the research) at a greater risk of harm (including physical, psychological, economic, or social harm) related to the research than was previously known or expected.

A UP must be reported within 7 calendar days of an investigator becoming aware of the actual or suspected UP.

5.3.2. Non-Compliance

Non-compliance is the failure of investigator(s) to follow the applicable laws, regulations, or institutional policies governing the protection of human subjects in research, or the requirements or determinations of the IRB, whether intentional or not.

Non-compliance may be unintentional (e.g. due to lack of understanding, knowledge, or commitment), or intentional (e.g. due to deliberate choice to ignore or compromise the requirements of any applicable regulation, organizational policy, or determination of the IRB).

Non-compliance is further characterized as serious or continuing as follows:

- Serious non-compliance - Non-compliance, whether intentional or not, that results in harm or otherwise materially compromises the rights, welfare and/or safety of the subject. Non-compliance that materially effects the scientific integrity or validity of the research may be considered serious non-compliance, even if it does not result in direct harm to research subjects.
- Continuing non-compliance – A pattern of recurring non-compliance that either has resulted, or, if continued, may result in harm to subjects or otherwise materially compromise the rights, welfare and/or safety of subjects, affect the scientific integrity of the study or validity of the results. The pattern may comprise repetition of the same non-compliant action(s), or different noncompliant events.

Any actual or suspected non-compliance by any investigator or entity associated with the protocol must be reported to the IRB by the PI/designee within 7 calendar days of any investigator or individual associated with the protocol first becoming aware.

5.3.3. Protocol Deviation

A protocol deviation is defined as any change, divergence, or departure from the IRB-approved research protocol and is further characterized as major and minor as follows:

- Major Deviations – Deviations from the IRB approved protocol that have, or may have the potential to, negatively impact, the rights, welfare or safety of the subject, or to substantially negatively impact the scientific integrity or validity of the study.

- Minor Deviations – Deviations that do not have the potential to negatively impact the rights, safety, or welfare of subjects or others, or the scientific integrity or validity of the study.

For the reporting purposes, failure of subjects to comply with the research protocol does not represent non-compliance unless that failure is due to an action or omission of a member of the research team, for example, the failure to give adequate instruction to the subject.

A major deviation must be reported within 7 calendar days of an investigator becoming aware of an actual or suspected deviation. Although PDs are also non-compliance, these should only be reported once as deviations. Major deviations resulting in death must be reported within 24 hours of the occurrence of the event or of any member of the study team becoming aware of the death.

Researchers are responsible for monitoring their studies throughout the year for adherence to the IRB-approved protocol. The purpose of this monitoring is to identify major deviations and to look for trends in minor deviations that may indicate a systemic issue in how the study is being conducted that could potentially negatively impact the rights, safety, or welfare of participants or the study's ability to produce scientifically valid results. A series of minor deviations pointing toward a more global issue that could affect the rights, safety or welfare of the participant or affect the validity of the study should be reported as a major deviation. In all other instances, a summary of minor deviations should be provided to the IRB at the time of continuing review.

